Title: Optimizing an mHealth Intervention to Change Food Purchasing Behaviors for Cancer
Prevention
NCT04947150
Document date: 3/25/21

Statistical Analyses

We will run repeated measures ANOVAs that examined whether outcomes change across time (i.e., from baseline to post-treatment). Models also include the interaction effects of each intervention component (location triggered messaging, benefits of change, coach monitoring, and household support) and time to determine whether these components could enhance change. Each condition variable is coded as 0=OFF or 1=ON, and all conditions are included in a single model for each outcome. We also report and interpret effect sizes (partial eta squared; η^2) in addition to *p*-values. Effect sizes are interpreted as meaningful if they are .06 or higher, indicating a medium effect. Post-hoc pairwise comparisons examine change in each guideline across time separately for each condition.

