Title: Optimizing an mHealth Intervention to Change Food Purchasing Behaviors for Cancer
Prevention
NCT04947150
Document date: 3/25/21

Protocol

Study Design

This study is a National Cancer Institute (NCI)-funded pilot, randomized controlled trial (R21CA252933) utilizing a factorial design to test the effect of four different intervention components on dietary intake and grocery store purchases. The four factors yield 16 different combinations of intervention components (Table 1). An equal number of participants were randomized to receive vs. not receive each of the four experimental intervention components. For example, half of participants have their food purchasing data monitored by a coach and half do not have this feature as part of their intervention. As another example, half of participants were randomly assigned to have household member involvement included in their intervention package, but this randomization was done independently of that for coach monitoring (i.e., the four experimental intervention components were not “bundled” together). Baseline covariates used for randomization included biological sex, body mass index (BMI), age, household size, and dietary adherence score.

Ethics Approval

This study was approved by the Drexel University Institutional Review Board (Study ID #2003007695) on March 13, 2021.

Participants, Eligibility, and Recruitment

The study enrolled 62 index participants, as well as 31 household members who are serving in a support role. Participants were recruited from the Philadelphia area in two cohorts via targeted mailings, social media outreach, and Craigslist listings, and was supported in part by community recruitment resources from Thomas Jefferson University’s Sidney Kimmel Cancer Center. Specifically, Jefferson’s Regional Liaison Office employed their “honest broker” system which aided in identifying and contacting potential participants using internal communication resources, community contacts, and other available resources (e.g., participants within the Jefferson community who matched eligibility criteria were emailed about their interest in participating). Interested individuals completed a screening survey and, if deemed preliminarily eligible, attended an information session via videoconferencing. After the session, those interested in participating attended a baseline assessment, in which their final eligibility was determined.

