Feasibility and acceptability

Feasibility and acceptability data are being collected and will be compared to pre-established benchmarks. Recruitment feasibility will be operationalized with a benchmark of >5 participants enrolled per month of recruitment and $<30\%$ of those otherwise interested/eligible refusing participation. Retention feasibility will be operationalized with a benchmark of $>70\%$ of participants completing each follow-up assessment. Feasibility and acceptability of food purchasing data will be operationalized with a benchmark of $>90\%$ of participants having food purchase digital data successfully captured. Feasibility for message delivery will be assessed by location-triggered messaging delivery, with successful receipt of messages measured by $<5\%$ of delivery encountering technological problems. User-rated acceptability will be measured by the benchmark of a mean rating >28 on the Treatment Acceptability Questionnaire (adapted, 8-items; 7-point Likert scale; given at 10 and 20 weeks). Qualitative information about acceptability will be collected via post-intervention focus groups. Focus groups will be audio recorded, transcribed, with responses coded for themes and patterns, and used to further refine the intervention for future testing.

Dietary intake

All participants complete dietary intake questionnaires at 0 and 20 weeks. Cohort 1 participants completed three days of food recalls at each time point, administered by the Automated Self-

Administered 24-hour Dietary Recall (ASA24), an NCI-designed software tool [86]. ASA24 is based on the well-validated automated multiple pass method, which has been shown to be as or more accurate than nutritionist-administered 24-hour food recall when using doubly labeled water as the criterion.

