After baseline administration of the ASA24, many Cohort 1 participants reported that they perceived this measure to be excessively burdensome. Due to the low acceptability, we replaced the ASA24 with the Diet History Questionnaire (DHQ-III) for Cohort 2 participants, due to its streamlined format and reduced completion time. The DHQ-III is a food frequency questionnaire developed by the NCI. The nutrient and food group database for DHQ-III is based on a compilation of national 24-hour dietary recall data from the National Health and Nutrition Examination Surveys. Cohort 2 participants completed the DHQ-III at baseline and will complete it again at 20 weeks. Given the different measures of dietary intake, differences in dietary intake variables across waves will be assessed and analyses on dietary intake will be conducted separately for each wave.

Both the ASA24 and DHQ-III provide item-level nutritional information for all food/drinks consumed as well as daily totals of various nutrient variables. For the NCI recommendation specific to highly processed food, food items will be flagged and included in this category based on those defined as highly processed based on the widely used NOVA classification system. Items in the processed food category include salty snacks, frozen and prepared meals, baked goods, dessert, fried potatoes, candy, packaged bread and buns, refined grains, breakfast cereal, processed cheese, etc. Relevant items that fall into this category are pulled from the ASA24 items-level output based on their Food and Nutrient Database for Dietary Studies (FNDDS) food code and from the DHQ-III items-level output based on their coding in the NCI's associated nutrient database and included in nutrient total calculations for processed foods. Similarly, sugar-sweetened drinks are identified in the ASA24 (based on their FNDDS food code) and DHQ-III (based on nutrient database) and used to calculate adherence to the relevant guideline. Sugar-sweetened drinks include non-diet sodas, non-diet fruit drinks, energy drinks, and sugary coffee drinks.

Average daily intake of the following items relevant to NCI dietary recommendations will be calculated from the ASA24 and DHQ-III:

1. Fiber: grams of fiber
2. Fruit and vegetables: cups of all fruit (intact whole or cut fruit not including fruit juices) and vegetables (all vegetables excluding starches)

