3. Added sugar from processed food: grams of added sugar consumed from items flagged as highly processed (as described above)
4. Saturated fat from processed food: grams of saturated fat consumed from items flagged as highly processed (as described above)
5. Sodium from processed food: milligrams of sodium consumed from items flagged as highly processed (as described above)
6. Red meat: ounces of beef, veal, pork, lamb, and game meat
7. Processed meat: grams of frankfurters, sausages, corned beef, and luncheon meat made from beef, pork or poultry
8. Sugar-sweetened drinks: ounces of sugar-sweetened beverages (as defined above)

Given that NCI dietary recommendations for red and processed meat are on the week (vs. daily) level, average daily intake of red and processed meat are prorated to reflect intake over 7 total days.

Scores for adherence in each domain of the NCI dietary recommendations are calculated based on the 0, 0.5, 1 cutoff values established previously, where 1 reflects fully meeting the recommended level of intake, 0.5 indicates partially meeting recommended levels, and 0 reflects failure to meet the recommendation. When guidelines include multiple sub-categories (e.g., fiber and fruits/vegetables), the guideline score was calculated as the average of adherence on sub-categories. Two overall adherence scores were calculated: 1) the sum of adherence on the four guidelines (range 0-4) and 2) average adherence on the four guidelines (range 0-1). The subscores are: a) average of adherence scores for fiber and fruits/vegetables, b) average of adherence scores for added sugar, saturated fat, and sodium in processed foods, c) average of adherence scores for red and processed meats, and d) adherence score for sugar-sweetened drinks.

As a secondary outcome for dietary intake, an adapted, 13-item Food Frequency Questionnaire is administered at baseline and 20 weeks. Each item pertains to one of the four dietary guidelines (e.g., “Whole grain products or high fiber starches”, “Red meats such as beef, pork, lamb”, “Non-diet sweet drinks”), and participants are instructed to report the frequency with which they ate the foods in the past month with a 6-point Likert-type scale (ranging from 0 - “never” to 5 - “twice or more per day”). Total guideline scores will be calculated as the average of responses to all items pertaining to that guideline (e.g., guideline 1 as the average of 0-5 response for fiber and 0-5 response for fruits/vegetables).

Mediators

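### The component-by-time test for diet is a change-score comparison; adjusting for baseline is more precise unless the slope on baseline is near 1, and costs one error degree of freedom

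*SAP*

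**What the plan says.** The SAP (Statistical Analyses) tests every outcome in one framework: "We will run repeated measures ANOVAs that examined whether outcomes change across time (i.e., from baseline to post-treatment"). On the components it says: "Models also include the interaction effects of each intervention component" and time. All four components, coded 0/1, enter a single model per outcome, and no baseline covariate is named. Partial eta squared is reported beside the p-value: "Effect sizes are interpreted as meaningful if they are .06 or higher, indicating a medium effect".

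The protocol (Dietary intake) gives two occasions for the recall or diet history measure, "All participants complete dietary intake questionnaires at 0 and 20 weeks", and two for the secondary measure, "an adapted, 13-item Food Frequency Questionnaire is administered at baseline and 20 weeks". Because the cohorts used different instruments, "analyses on dietary intake will be conducted separately for each wave". Study Design says: "Baseline covariates used for randomization included biological sex, body mass index (BMI), age, household size, and dietary adherence score". It does not describe the allocation mechanism.

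**The concern.** A two-occasion repeated measures ANOVA tests whether mean change differs between participants with and without a component. That amounts to subtracting the baseline value with a coefficient of exactly 1. When the 20-week value tracks baseline with a smaller slope, the subtraction adds baseline noise that a fitted slope would remove.

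This trial has little precision to spare. It has 62 index participants, diet is analysed by wave, and the retention benchmark (more than 70% at each follow-up) allows for substantial dropout. The baseline value is already collected. At stake is some power for each component test and, when an effect is real, some of the chance of reaching the .06 line.

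The dietary adherence score also helped determine allocation. If allocation tightly balanced that score, the planned test of it has a standard error that is too large and rejects less often than its nominal level.

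**Working it through.** The documents give no power, alpha, SD or correlation, so there is no planned figure to reproduce.

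**Inputs from the documents.** 62 index participants in two cohorts; four 1:1 factors in one model; diet at weeks 0 and 20; analysis by wave; retention benchmark above 70%; partial eta squared line .06.

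**Assumptions.** 31 per wave (62/2); 22 completers per wave (31 × 0.70 = 21.7) and 44 overall (62 × 0.70 = 43.4), both rounded up; effect 0.5 baseline SD; correlation ρ from .3 to .9; two-sided 5%; normal outcomes; simple 1:1 allocation unless stated.

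**Step 1: equivalence.** On one simulated data set (n = 62, four factors), the component-by-time F values and the squared t values from regressing change on the four components were identical: 1.735, 0.018, 5.047 and 0.063, on 62 − 5 = 57 error df. Adding baseline leaves 56. At n = 31 the step is from 26 to 25.

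**Step 2: precision.** Let r = SD20/SD0, so the slope is ρr. Then

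Var(change) = residual variance + (1 − slope)² × baseline variance.

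With equal SDs, Var(change) = 2(1 − ρ)s² and the adjusted variance is (1 − ρ²)s². The SE ratio is √(2/(1 + ρ)) = 1.240, 1.155, 1.085 and 1.026 at ρ = .3, .5, .7 and .9.

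With unequal SDs the ratio is √[(1 + r² − 2ρr) / (r²(1 − ρ²))]. Over r from 0.8 to 1.25 and ρ from .3 to .9:
- Largest, at ρ = .3, r = 0.8: √(1.16/0.5824) = 1.41.
- Smallest, for example at ρ = .8, r = 1.25 (slope 1): √(0.5625/0.5625) = 1.00.

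**Step 3: power.** 20,000 simulated trials per setting, planned → baseline-adjusted, equal SDs:

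| N | ρ = .3 | ρ = .5 | ρ = .7 | ρ = .9 |
|---|---|---|---|---|
| 22 | 14 → 18% | 18 → 21% | 26 → 28% | 63 → 62% |
| 31 | 19 → 25% | 25 → 30% | 37 → 41% | 81 → 81% |
| 44 | 26 → 37% | 34 → 43% | 53 → 58% | 94 → 94% |
| 62 | 36 → 50% | 47 → 57% | 69 → 74% | 99 → 99% |

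With unequal SDs at N = 31 and ρ = .7, power goes from 42 to 58% at r = 0.8, but from 29 to 28% at r = 1.25, where the slope is .875. A separate noncentral-t calculation gave slightly higher power throughout (27 → 33% at N = 31, ρ = .5) and gains of similar size. It puts the equal-SD break-even slope at about 0.92 for N = 31 and 0.97 for N = 62.

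**Step 4: validity.** With no effect at N = 31 the planned test rejects in 4.7 to 5.1% of trials and the adjusted test in 4.9 to 5.3%.

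Under an assumed tight balancing of allocation on five covariates including the baseline score (6,000 trials), the planned test rejects in 2.0, 3.0 and 3.3% at ρ = .3, .5 and .7, against 4.6, 5.0 and 5.2% adjusted. At ρ = .5 the planned model reports an SE of .390 when the true SE is .341.

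**Step 5: the .06 line.** At N = 31 with a real effect, the chance that partial eta squared reaches .06 goes from 53 to 61% (ρ = .5) and from 66 to 71% (ρ = .7). With no effect it is about 21% planned and 22% adjusted.

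**Step 6: all five covariates.** If the four extras (sex, BMI, age, household size) are uninformative, power at ρ = .5, .7 and .9 is 26, 36 and 74% at N = 31 (planned 25, 37 and 81%), and 17, 22 and 49% at N = 22 (planned 18, 26 and 63%). At ρ = .5, to beat baseline-only adjustment the extras together must explain between 10 and 20% of the remaining variance at N = 31, and between 20 and 30% at N = 22.

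**The case against.** The planned test is unbiased, keeps its false-positive rate under simple allocation, and directly answers the SAP's question of whether components enhance change. Within a wave the equal-SD gain is 4 to 6 points of power at N = 31 and 2 to 4 at N = 22 for ρ up to .7, and nothing at .9. Power stays low either way, and this is a pilot that claims none. All of that stands, and it is why the point is a suggestion and not an error.

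The rows for 44 and 62 matter for diet only if some outcome is analysed on all participants. The 13-item questionnaire is a candidate because it is the same instrument at both times, so the protocol's reason for splitting does not apply to it. But the protocol lists it under dietary intake, and a literal reading splits it too. Those rows are conditional.

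The inputs are assumed, and outcomes were simulated as normal although the adherence score is built from 0, 0.5 and 1 cut-offs. This limits confidence in the size of the gain, not in the equivalence or the one-df cost.

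Partial eta squared also changes scale. At ρ = .5 with equal SDs, .06 corresponds to √(4 × (.06/.94) × 1.00) = 0.51 SD under the planned model and √(4 × (.06/.94) × 0.75) = 0.44 SD after adjustment. Part of the higher crossing rate is therefore a lower bar on the raw scale. The no-effect crossing rate barely moves, so this does not undo the recommendation, but readers should be told.

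**Conclusion.** The point holds as an efficiency improvement worth considering. For the diet outcomes the equivalence to a change-score test and the cost of one error df are exact. They do not extend to outcomes also measured at week 10. The gain depends on quantities the documents do not give: over the ranges examined, the planned SE is between 0 and 41% larger. In a wave of about 31 the gain is modest and can vanish at slopes somewhat below 1. It is larger for any outcome analysed on all participants. Adjustment does not cure chance crossings of .06. Whether the planned test is also conservative for the adherence score depends on the unstated allocation mechanism.

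**What to change.** - Within each wave, test component effects by regressing the 20-week value on the four component indicators and the baseline value of that outcome. Do the same for the 13-item questionnaire, and say whether it is pooled across waves.
- Keep the repeated measures ANOVA for overall change over time and the post-hoc comparisons by condition, and as a sensitivity analysis for component effects.
- Add sex, BMI, age or household size only as a short list fixed before outcome data are seen and expected to predict the outcome. Adjusting for all five randomization covariates by default is not advised within a wave.
- State which model the .06 line is read from.
- State the allocation mechanism, so readers can judge whether the planned test is conservative for the balanced score.

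The cost is SAP wording and one error degree of freedom per model. No new data are needed.

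### The planned repeated measures ANOVA drops by default anyone without a week-20 value, which biases mean change if dropout depends on baseline; a mixed model keeps every baseline

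*SAP*

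**What the plan says.** The SAP (Statistical Analyses) names one method: "We will run repeated measures ANOVAs that examined whether outcomes change across time (i.e., from baseline to post-treatment"). The four component-by-time interactions enter together, since "all conditions are included in a single model for each outcome". Results are judged by p-values and by partial eta squared, with .06 as the threshold for a meaningful effect.

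The protocol fixes the data that this model receives:

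- Participants, Eligibility, and Recruitment: "The study enrolled 62 index participants, as well as 31 household members who are serving in a support role".
- Study Design: "An equal number of participants were randomized to receive vs. not receive each of the four experimental intervention components".
- Measures, Dietary intake: "All participants complete dietary intake questionnaires at 0 and 20 weeks". Cohort 1 used the ASA24 and Cohort 2 the DHQ-III, and "analyses on dietary intake will be conducted separately for each wave". Cohort sizes are not given.
- Measures, Feasibility and acceptability: retention succeeds if more than 70% "of participants completing each follow-up assessment".

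Neither document gives an analysis population, a rule for missing follow-up, an imputation, a likelihood-based analysis or a sensitivity analysis.

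**The concern.** With two time points, the time and component-by-time tests in a repeated measures ANOVA are tests on the difference between week 20 and baseline. Without a week-20 value there is no difference, so as usually fitted the model deletes that person, including the baseline already observed. Nothing in the text overrides this.

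Deletion matters because baseline predicts change. When baseline and follow-up correlate less than perfectly, low scorers tend to rise and high scorers to fall. If those who leave are not typical at baseline, the completers' mean change differs from that of everyone randomised. If the selection also differs between ON and OFF of a component, the difference carries into that component's contrast with time, which is the comparison the factorial design was built to make. The dietary models are fitted within wave, so each loss falls on a smaller sample than 62.

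**Working it through.** **1. Stated figures.** The documents give no sample-size calculation and no dropout, SD or correlation assumption, so there is no planned figure to reproduce.

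**2. Loss compatible with the benchmark.** 44/62 = 70.97% passes and 43/62 = 69.35% fails. At most 62 - 44 = 18 people (29%) can be missing at week 20 with retention still met. This is a ceiling over both cohorts.

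**3. Bias in mean change.** With equal SDs at both times, correlation rho and dropout that depends on baseline:

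bias = (rho - 1) x (mean baseline of completers - mean baseline of all), in baseline SD.

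Assumptions: normal baseline; logistic dropout with log-odds rising 0.5 or 1.0 per SD lower baseline; rho 0.3 to 0.7. At 44/62 retention, numerical integration puts the completers' baseline 0.138 SD too high (slope 0.5) or 0.245 SD too high (slope 1.0).

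| rho | slope 0.5 | slope 1.0 |
|---|---|---|
| 0.3 | -0.7 x 0.138 = -0.10 | -0.7 x 0.245 = -0.17 |
| 0.5 | -0.5 x 0.138 = -0.07 | -0.5 x 0.245 = -0.12 |
| 0.7 | -0.3 x 0.138 = -0.04 | -0.3 x 0.245 = -0.07 |

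With slope 0 the bias is 0. With the slope reversed the sign reverses.

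**4. Bias in a component-by-time contrast.** Apply the same formula within ON and OFF and subtract: (rho - 1) x (completers' baseline shift ON - shift OFF). Sizes below ignore the sign, which depends on which group loses more.

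- 20% versus 25% dropout: shifts 0.096 and 0.120 (slope 0.5), 0.173 and 0.213 (slope 1.0). The differences are 0.023 and 0.040. Multiplied by 0.3 to 0.7, they give 0.007 to 0.028 SD.
- 15% versus 40% dropout: shifts 0.073 and 0.189, 0.133 and 0.332. The differences are 0.117 and 0.200, giving 0.035 to 0.140 SD. Average dropout is 27.5%, so the retention benchmark would still be met.
- Equal rates and equal dependence on baseline: difference 0, bias 0.

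**5. Against the SAP's threshold.** Partial eta squared .06 gives f = sqrt(.06/.94) = 0.253. That is 0.253 change-score SD for mean change and 2 x 0.253 = 0.505 for an ON-OFF contrast. The change-score SD is sqrt(2(1 - rho)), or 1.18, 1.00 and 0.77 baseline SD for rho 0.3, 0.5 and 0.7. The mean-change bias is therefore 21% (0.0415/0.775/0.253) to 57% (0.1716/1.183/0.253) of a threshold-sized effect. The contrast bias is about 2% to 5% at 20% versus 25%, and about 9% to 23% at 15% versus 40%.

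**6. Simulation** (62 people, four 1:1 factors, rho 0.5, slope 1.0, about 29% dropout, 4,000 runs; true mean change 0.40 SD, true contrast 0):

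| Dropout depends on baseline | Change, completers | Change, likelihood | Contrast, completers | Contrast, likelihood |
|---|---|---|---|---|
| equally ON and OFF | 0.276 | 0.398 | -0.001 | -0.001 |
| ON only | 0.339 | 0.400 | -0.118 | 0.003 |

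The first row agrees with step 3: 0.40 - 0.12 = 0.28. The likelihood estimator kept all 62 baselines and did not constrain baseline means across components.

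**7. Precision.** At partial eta squared .06 and an assumed two-sided alpha of 0.05, power for one component-by-time term is about 0.50 with 62 people and 0.37 with 44. No model fully restores the missing outcomes.

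**The case against.** Several points on the other side stand.

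- **Deletion is inferred from the method.** The SAP does not say that it will analyse completers only, and the same ANOVA after multiple imputation would not contradict it. But no imputation is planned, and deletion is what the named method does unless something is added.
- **Unequal burden is weaker than the contact ranges suggest.** A reader might take the 3 to 5 sessions and 0 to 9 calls as the gap between ON and OFF. They span all 16 combinations. For a single component, the largest scheduled gap is one extra 60-minute session and three 20-minute calls (benefits of change, household support). Coach monitoring adds three calls and weekly messages; location triggering adds no session or call. Nothing in the documents supports a 15% versus 40% split, which is an illustration only.
- **The burden complaint concerned Cohort 1.** Cohort 2 was given a shorter instrument for that reason, so the complaint is not evidence of high dropout there.
- **Sampling error is larger.** At 15% versus 40% in 62 people (about 26 and 19 completers), the contrast's standard error is 0.23 to 0.36 SD. The bias is 0.15 to 0.39 of that, and this is a pilot. For mean change with 44 completers, the standard error is 0.12 to 0.18 SD and the bias about 0.36 to 0.96 of it. Mean change is more exposed, but it is an uncontrolled pre-post quantity. In the scenario assumed here, the error understates improvement on an adherence score.

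These points limit the size of the problem, chiefly for the contrasts. They do not remove the default deletion.

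**Conclusion.** The point holds in a limited form. The named method discards by default anyone without week 20, and nothing planned compensates. The bias in mean change is about -0.04 to -0.17 baseline SD at 29% dropout. That figure rests wholly on the assumed correlation, dropout strength and direction, none of which the documents give. For the component contrasts, bias needs dropout, or its dependence on baseline, to differ between ON and OFF. It is 0.01 to 0.03 SD for a modest difference in rates and reaches 0.14 SD only under the assumed 15% versus 40%.

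Two stronger readings are not supported. The first is that 18 people will be lost, or lost from a dietary model. The 18 is a pooled ceiling implied by a feasibility benchmark, which is neither a dropout forecast nor an analysis rule, and the loss per wave cannot be worked out. The second is that the randomised comparison is lost: with dropout related to baseline equally ON and OFF, the contrasts remain unbiased. The change is still worth making, because a method that keeps every baseline needs no new data.

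**What to change.** Replace the repeated measures ANOVA with a linear mixed model fitted by REML to all randomised index participants with at least one assessment, within wave for dietary intake. Use an unstructured covariance over time and constrain the baseline mean to be equal across components, as randomisation justifies. Keep the four component-by-time terms in one model per outcome. Report missing week-20 data by component, ON and OFF. The model removes the bias only when dropout depends on observed data such as baseline and component, so add a sensitivity analysis in which dropout depends on the unobserved week-20 outcome.

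The cost is SAP wording and modest extra analysis. One consequence needs handling: partial eta squared is not a direct output of a mixed model. Either report a standardised effect with its confidence interval and restate the .06 threshold on that scale, or keep the ANOVA as a supporting complete-case analysis, labelled as such.

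### The SAP fixes 0/1 coding but not the contrast, so its Time test can target the predicted all-OFF change, with about five times the variance of the average change

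*SAP*

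**What the plan says.** The SAP (Statistical Analyses) plans "repeated measures ANOVAs that examined whether outcomes change across time (i.e., from baseline to post-treatment"). On the rest of the model it says "Models also include the interaction effects of each intervention component" with time. No component-by-component term is named, so as written the model for change is additive in the four components. The coding rule is "Each condition variable is coded as 0=OFF or 1=ON, and all conditions are included in a single model for each outcome". Results are judged by p-value and by partial eta squared: "Effect sizes are interpreted as meaningful if they are .06 or higher".

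The SAP does not say whether the 0/1 variables are numeric covariates or between-subject factors. It names no contrast, centring or sum-of-squares type, and does not define what the Time effect estimates.

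The Protocol (Study Design) describes a factorial trial: "The four factors yield 16 different combinations of intervention components", and "An equal number of participants were randomized to receive vs. not receive each of the four experimental intervention components". Under Participants, Eligibility, and Recruitment it says "The study enrolled 62 index participants". Under Dietary intake, the two cohorts used different instruments and are to be analysed separately.

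**The concern.** In a model with interactions, what a lower-order term means depends on how the other variables are coded. With 0/1 values entered numerically, the Time term is the change when every component equals 0. That is one of 16 combinations, the basic package alone. The natural reading of the SAP's first question is the change over the trial as a whole, although the SAP does not use those words.

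The p-value and partial eta squared for Time could therefore answer a different question from the one asked, and much less precisely. If the components work, the all-OFF change is also smaller than the average change. Two analysts following the same text could report different Time results from the same data, and the SAP's .06 rule could class one as meaningful and the other not.

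**Working it through.** **Inputs from the documents.** N = 62; 16 combinations; half ON for each component (31 and 31); 0/1 coding; threshold .06. Contact-time splits (Protocol, Experimental intervention components and contact time): 26/48/26% for 3/4/5 sessions, and 18/29/39/14% for 0/3/6/9 calls. These fit about 16/30/16 and 11/18/24/9 of 62.

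**Assumptions.** Two-sided alpha 0.05 and the size of change, expressed in SDs of the change score. The documents give no alpha, SD, target effect or power calculation, so there is no planned figure to reproduce.

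**Step 1: reduce the model.** With two time points, Time and the component-by-time terms are equivalent to a regression of the change score on the four components. Time is the intercept.

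**Step 2: what the intercept estimates.** Write expected change as b0 + Σ bj·xj.
- Numeric 0/1: the intercept is b0, the predicted all-OFF change.
- −1/+1 numeric, or centred: the intercept is b0 + ½Σ bj, the average over the design.

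The two differ by half of each component's effect.

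**Step 3: variance in the balanced additive model.**
- Effect-coded: σ²/N = σ²/62 = 0.0161σ².
- 0/1: (σ²/N)·[1 + 4 × (0.5²/0.25)] = 5σ²/62 = 0.0806σ².
- Ratio 5.0; SE ratio √5 = 2.24; effective n = 62/5 = 12.4.

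**Step 4: actual allocation.** The cell counts are not given, so three approximations were used.
- Covariances implied by the contact-time splits, with location triggering taken as uncorrelated: ratio about 4.5.
- 300 random allocations of 62 matching those splits: 3.7 to 6.7, mean 4.6.
- 5,000 random allocations with only 31 ON per component fixed: median 5.1, 95% range 4.1 to 6.8.

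**Step 5: effect on the Time test.** Assume the same change d in every cell (so only precision differs), N = 62 and 62 − 5 = 57 df. Then t = d√62 (effect-coded) or d√12.4 (0/1), and partial eta squared = t²/(t² + 57).

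| d (SD) | t, effect-coded | ηp² | Power | t, 0/1 | ηp² | Power |
|---|---|---|---|---|---|---|
| 0.3 | 2.36 | .089 | 64% | 1.06 | .019 | 18% |
| 0.4 | 3.15 | .148 | 87% | 1.41 | .034 | 28% |
| 0.5 | 3.94 | .214 | 97% | 1.76 | .052 | 41% |

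The change detectable with 80% power is 0.36 SD against 0.81 SD.

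**Step 6: adding the shift in target.** If the average change is 0.5 SD and each component adds 0.1 SD, the all-OFF change is 0.5 − 4 × 0.1 × 0.5 = 0.3 SD. The 0/1 result is then the first row: ηp² .019, power 18%.

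**Step 7: dietary intake.** These models have fewer than 62 people, and cohort sizes are not given. With an assumed 31 per cohort and d = 0.5, power is 76% against 22%, and the detectable change 0.52 SD against 1.17 SD. The balanced ratio of 5 does not depend on N.

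**Step 8: component-by-time tests.** In a simulated balanced dataset the component-by-time t-statistic had the same size (0.326) under both codings.

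**The case against.** The strongest reply is that 0/1 may be only a value label. If the components are declared as between-subject factors with sum-to-zero contrasts and Type III tests, Time already tests the average change. In sequential tests with Time first, or in Type II tests, Time is not adjusted for the interactions and coding has no effect. The references to repeated measures ANOVA and partial eta squared, and the planned post-hoc comparisons within each condition, fit factor entry. Naming only component-by-time terms fits numeric entry. Neither settles it. This objection stands: a reader might infer that the SAP does test the all-OFF change, but the text only leaves that possible.

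Three other inferences are also unsupported.
- **That Time would rest on about 4 people.** The nominal cell is 62/16 = 3.9, and the 11 people with no calls suggest about 5 to 6 all-OFF if location triggering splits them evenly. But the additive model's prediction uses all 62 people, hence the factor of 5. A factor of 16 belongs to the raw cell mean or a saturated 0/1 model, which the SAP does not describe.
- **That relabelling to −1/+1 is enough.** In a simulated balanced design of 64 records, −1/+1 values declared as factors with reference-cell contrasts still gave the all-OFF prediction (0.655, SE 0.239), not the mean (0.427, SE 0.107). The contrast decides, not the label.
- **That a real change would necessarily fall below .06.** With 0/1 coding at 5/N, 0.55 SD gives 3.751/60.751 = .062. At 0.5 SD, variances of 3.7/N to 6.7/N give .069 to .039.

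It is also fair that the trial's stated purpose is to test the components, and those tests are untouched.

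**Conclusion.** The point holds as a conditional one. The SAP leaves the Time estimand and contrast undefined, and its only stated rule permits an analysis in which Time is the predicted all-OFF change. In that case the variance is 5 times that of the average change in the balanced additive model, and about 4 to 7 times under plausible allocations. The estimate also leaves out half of each component's effect. The partial eta squared and power figures are illustrations under an assumed effect, alpha and N = 62, not predictions for this trial. Exposure is limited to the overall Time test and its effect size. The documents do not show that the wrong analysis will be run, but the ambiguity costs nothing to remove.

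**What to change.** Replace the SAP's coding sentence with:

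> Components are effect-coded (−1 = OFF, +1 = ON, entered as numeric variables, or equivalently as factors with sum-to-zero contrasts and Type III tests), so that the Time effect is the average change over all component combinations.

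The way the variables are entered must be stated along with the values, because the values alone do not fix the contrast. If the change under the basic package alone is of interest, report it as a separate labelled contrast with its own standard error.

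The cost is one sentence. No new data are needed, and the component-by-time tests do not change.
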